8.4 Serious Adverse Event Reporting Procedures

Serious adverse events that occur beginning with the first day of the study drug administration, during treatment, or within 30 days of the last dose of treatment, or up to study end point must be reported to the Cleveland Clinic Principal Investigator.

Investigative sites will report serious adverse events to their respective IRB according to the local IRB's policies and procedures in reporting serious adverse events.

8.4.1 FDA Reporting

N/A

8.5 Data Safety Toxicity Committee

It is the *Case Comprehensive Cancer Center* Principal Investigator's responsibility to ensure that ALL serious adverse events are reported to the Case Comprehensive Cancer Center's Data Safety Toxicity Committee. This submission is simultaneous with their submission to other Regulatory body.

9.0 PHARMACEUTICAL INFORMATION

A list of the adverse events and potential risks associated with the investigational or commercial agents administered in this study can be found in Section 8.0.

9.1 Investigational Agents

N/A

9.2 Commercial Agents

Agents are listed in alphabetical order.

9.2.1 Methotrexate (NSC #740)

Chemical name: Methotrexate

Formulation:	Methotrexate is available as the sodium salt for parenteral use in 20 mg, 50 mg, and 1 g vials as the lyophilized powder. Liquid methotrexate sodium injection products, and tablets for oral administration are also available.
Toxicity:	Adverse reactions include dizziness, drowsiness, general body discomfort, headache, loss of appetite, mild hair loss, mucositis, nausea, vomiting, diarrhea, myelosuppression, skin rashes, itching, pigmentation changes, impaired renal and hepatic function.
Manufacturer:	Immunex
Supplier:	Patient or 3 rd Party
Mechanism of Action:	Methotrexate is an antimetabolite and has its principle mechanism of action the competitive inhibition of dihydrofolate reductase.

9.2.2 Mycophenolate (NSC #61443)

Chemical name:	Mycophenolate mofetil
Formulation:	Mycophenolate is available in capsule form, 250 mg or tablets of 50mg. Liquid forms are also available and come in 500 mg vials (20 mL).
Toxicity:	Adverse reactions include anxiety, back pain, constipation, diarrhea, dizziness, headache, loss of appetite, leukopenia, sepsis, nausea, vomiting, tremor, trouble sleeping and increased incidence of infections.
Manufacturer:	Roche
Supplier:	Patient or 3 rd party
Mechanism of Action:	Mycophenolate is rapidly absorbed following oral and IV administration and hydrolyzed to form MPA, which is the active metabolite. MPA is a potent, selective, uncompetitive and reversible inhibitor of inosine monophosphate dehydrogenase (IMPDH), and therefore inhibits the de novo pathway of guanosine nucleotide synthesis without incorporation into DNA. Because T- and B-lymphocytes are critically dependent for their proliferation on de novo synthesis of purines whereas other cell types can utilize salvage pathways, MPA has potent cytostatic effects on lymphocytes. MPA inhibits proliferative responses of T- and B-lymphocytes to both mitogenic and allospecific stimulation.

9.2.3 Tacrolimus (NSC #77865)

Chemical name:	FK506
Formulation:	Capsule, oral: 0.5 mg, 1 mg, 5 mg. Injection, solution: 5 mg/ml (1 ml).

Toxicity:	Adverse reactions include back pain, constipation, diarrhea, dizziness, headache, joint pain, loss of appetite, nausea, stomach pain or upset, trouble sleeping, vomiting, weakness.
Mechanism of Action:	Binds to the FKBP-12 protein and forms a complex with calcium-dependent proteins, thereby inhibiting calcineurin phosphatase activity and resulting in decreased cytokine production. This agent exhibits potent immunosuppressive activity and prevents the activation of T-lymphocytes in response to antigenic or mitogenic stimulation.

10.0 **CORRELATIVE / SPECIAL STUDIES**

10.1 **Research Sample Repository**

The purpose of this correlative study is to improve our understanding of GVHD by storing samples of blood/tissue of the recipient to use in various laboratory studies.

10.1.1 **Background and Rational:**

GVHD is a complex disease which arises when donor T cells respond to genetically defined and disparate proteins on host cells; the most important of which are human leukocyte antigens (HLAs), which are highly polymorphic and are encoded by the major histocompatibility complex (MHC). GVHD is often associated with a graft versus leukemia (GVL) effect, but separating the two is often a challenge. The pathogenesis underlying GVHD is a complex, multi-step process. There are many factors which are not fully understood which determine whether GVHD occurs and the strength of the reaction. These include the type and properties of transplanted T cells, histocompatibility antigen mismatching, interactions between T cells and endothelial cells, signaling events occurring between immune cells, induction of pro-inflammatory cytokines, and amount of B lineage-specific progenitor cells. Acute GVHD requires the early trafficking of donor naive T cells to recipient secondary lymphoid tissue where they undergo activation and expansion, and their subsequent migration to target organs where they elicit injury [15-17]. The study of these processes through laboratory studies including the measurement of cytokine production and cytokine receptors, determination of hematopoietic cell subtypes by flow cytometry, and determination of HLA antigen types by genotyping may help elucidate and separate the detrimental and beneficial effects conferred by donor-derived T cells and improve our understanding of GVHD.

10.1.2 **Patient Selection:**

Cleveland clinic patients enrolled in the trial may be asked to participate in this study to collect blood and tissue samples for laboratory research purposes.

10.1.3 Research Plan/Study Parameters:

Research in graft versus host disease depends on the ready availability of samples of blood, tissue (skin, GI tract, and liver biopsies) and bone marrow of transplant recipients and donors for *in vitro* studies. Assays may include phenotypic analysis by flow cytometry and histochemical methods, molecular biologic determination of specific DNA and RNA species, and gene expression analysis.

In addition, repositories of plasma, serum, DNA, RNA and whole cell preparations may be invaluable in retrospective analysis. Correlation of clinical data, such as age, sex, laboratory results, cytogenetics, bone marrow morphology, treatment, progression, co-morbidities, etc. may be used as needed. This data will only be linked to research sample number.

Recipients will have 10ml of peripheral blood obtained by venipuncture in 1 green top heparinized tube for a baseline specimen prior to transplantation. If a bone marrow specimen is performed, a 10 ml aspirate sample in a green top tube will be collected at that time. After transplantation, 10-20 ml (in 1-2 green top heparinized tubes) of peripheral blood may be obtained around transplant day +100 (+/-14 days), +180 (+/-30 days)(or time of immunosuppression withdrawal), and +365 (+/-30 days) through the patient's central venous catheter or by venipuncture. Additional blood samples from patients may be collected at time of clinical diagnosis or biopsy-proven GVHD.

If possible, with the development of GVHD some of the biopsy specimens from the organ involved (including skin, liver, or GI tract biopsy) may also be further assessed if there is adequate tissue.

For those patients who require a donor lymphocyte infusion (DLI) or subsequent infusion of additional hematopoietic stem cells post-transplant a follow-up peripheral blood sample will be obtained prior to procedure as well as again around day +100 (+/-14 days), and +365 (+/-30 days) after re-infusion.

The collection of ALL blood AND tissue specimens for the sample repository will only be collected when clinical specimens are collected to minimize patient discomfort.

10.1.4 Specimen Handling:

Tissue:

Biopsy material (bone marrow or GVHD affected tissue) may be frozen in liquid nitrogen and stored indefinitely at -80°C for molecular genetic studies if required as deemed by specific study. Otherwise, routine specimen fixation (in formalin and other appropriate fixates) for conventional histology and immunohistochemistry/FISH, preservation in tissue culture media for flow cytometry, and analysis of fresh sterile tissue for cytogenetics. Post-procurement processing on both frozen and formalin-fixed paraffin-embedded tissues will be performed. Derivative DNA and RNA may be extracted on these tissue samples for relevant assays for investigators.

Blood:

The protocol for blood processing and storage is as follows: Peripheral blood will be obtained in green top heparinized tubes. For each 10 ml of whole blood, approximately 4-5 ml of serum or plasma can be derived. These will be divided into 0.5 ml aliquots. Excess mononuclear cells will be frozen and stored in aliquots for flow cytometric analysis or DNA extraction. Glycerol will be added to a final concentration of 10% (w/v) as a cryoprotectant and specimens will be frozen at -80°C in aliquots of 10 ml and stored until use.

Specimens will be collected after the patient signs the written, informed consent. Specimens will only be obtained at the time routine clinical specimens are collected to minimize patient discomfort. Patients may refuse collection of specimens at any time. Specimens will be stored indefinitely or until a patient withdraws from the study.

DNA/blood samples from all BMT donors are stored in a registry under IRB 09-591 Allogen Laboratories Registry/Database. These specimens/data may be shared/tested/combined with this study to gain additional information.

10.1.5 Privacy Protection:

Specimens allocated to this research project will be assigned a research ID number, which will be the only identifier provided to investigators when they are given specimens. The key linking the research ID number with the patient identification (name, CCF ID number and date of birth) will be located in OnCore which is a secured, password protected database. Occasionally chart review will be necessary. For this purpose, a Co-Investigator will be provided with patient name and ID number for the purpose of abstracting pertinent historical information. The information will be recorded with only the research ID number.

10.1.6 Types of Laboratory Studies to Be Performed:

Blood, surgical specimens and bone marrow from patients may be utilized for diverse purposes. DNA/blood samples from all BMT donors are stored in a registry under IRB 09-591 Allogen Laboratories Registry/Database. These specimens/data may be shared to gain additional information.

This includes studies of hematopoiesis and immune reconstitution, measurements of cytokine production and cytokine receptors; determination of hematopoietic cell subtypes by flow cytometry and identification of T cell repertoire and antigens. Some studies may be genetic in nature, as for example determination of HLA antigen types by genotyping. Cells as well as serum are often banked for several years for future studies, the nature, which cannot be precisely predicted. However, the following list consists of examples of research that is currently performed on blood, surgical specimens and bone marrow:

- Using Flow cytometry analysis for proteins on the surface or inside of cells.
- Using flow cytometry and cell culture techniques to identify lymphocyte types and their function in disease including TCR usage and cytokine secretion phenotype.

- Measuring immunity to malignant cells, normal cells, viruses, bacteria, and fungi using flow cytometry, PCR techniques, cytokine release assays, proliferation assays and cytotoxicity assays. Some techniques will require culture of cells for several weeks.
- Detection of viral DNA or RNA.
- Correlation of clinical data, such as age, sex, laboratory results, cytogenetics, bone marrow morphology, treatment, progression, transfusion requirements, past medical history, co-morbidities, etc. as needed for future projects. These data will only be linked to the research sample number.
- Gene expression analysis.
- Immunohistochemistry for proteins expressed in or on the surface of cells.
- Analysis of chromosomal defects using array-based comparative and other molecular methods.
- Analysis of discrete changes in the DNA sequences derived from blood, tissue, and bone marrow using high density SNP arrays:
 - SNP genotyping in blood and marrow
 - SNP array-based karyotyping in blood and marrow

These studies do not include any therapeutic manipulations.

10.1.7 Risks:

The risks of this trial are minimal to patients. Transplant patients will have central venous catheters in place from which most of their blood specimens can be obtained, thus avoiding the potential minor discomfort from venipuncture. No bone marrow aspirations/biopsies or surgeries/tissue biopsies will be performed solely for research purposes. They will only be performed if already medically indicated.

11.0 STUDY PARAMETERS AND CALENDAR

11.1 Study Parameters

11.1.1 Pre-Study

All evaluations must be completed < 42 days prior to administration of myeloablative conditioning regimen given for allogeneic hematopoietic stem cell transplant.

- Informed consent
- Demographics
- Medical history
- Complete physical exam
- Disease assessment of tumor or site involved including bone marrow biopsy and aspirate
- Performance status (ECOG for adults, Lansky for pediatrics)
- Laboratory studies:
 - Complete blood count (CBC) with differential

- Hepatic enzymes: AST,ALT, alkaline phosphatase, total bilirubin, creatinine
- β -HCG for women of childbearing potential
- PT/PTT
- Pulmonary function testing with DLCO if pt > 6 years of age
- CMV screening
- HIV screening

See Study Parameters Table for specific time points for study assessments

11.1.2 During hospitalization for Transplant

- Laboratory studies:
 - Complete blood count (CBC) with differential
 - Hepatic enzymes: AST,ALT, alkaline phosphatase, total bilirubin, creatinine
 - PT/PTT
- CMV DNA testing
- Mucositis grading
- Acute GVHD monitoring
- Organ toxicity assessment
- Peripheral blood chimerisms (approximately 1, 2, 3, 6, 9 and 12 months or as clinically indicated)

See Study Parameters Table for specific time points for study assessments

11.1.3 Post hospitalization for Transplant to End of Study

Same assessments as above (during hospitalization for transplant); See Study Parameters Table for specific time points for study assessments

11.1.4 Study Parameters Table

Required Assessments	Pre-study (< 42 days prior Allo-HSCT)	During Initial Hospitalization for Allo-HSCT	Post Hospitalization for Allo-HSCT to Study End Point
Tumor characteristics / Site of involvement	X		As clinically indicated
ECOG / Lansky	X		Q visits until 1 year
Bone Marrow Aspirate / Biopsy	X		Day 100 (optional) or as clinically indicated
CBC and diff	X	Daily until ANC >500, plt >20,000, then Q weekly until normal	Q weekly until day 100 and then at follow up visits
Hepatic enzymes (AST, ALT, Alk Phos, Total Bili)	X	Daily until discharge	At follow up visits
Creatinine	X	Daily until discharge	At follow up visits
PT/PTT	X	Q weekly	As clinically indicated
CMV DNA	X	Q weekly	Weekly until D 100, then as clinically indicated
HIV screening	X		
PFT studies (> 6yo)	X		day 100 and as needed
PB chimerism		X (if patient is still in hospital at any time point)	Approximately 1, 2, 3, 6, 9, 12 months or as clinically indicated
HCG (female of childbearing age)	X		
Tac levels		2X / week or as clinically indicated	As clinically indicated
Acute GVHD Monitoring		1X / week starting D +7	Q weekly until day 100
Chronic GVHD monitoring			After D 100, at least every 3 months
Mucositis grading		3X / wk D 0 to D +28 or D/C (which ever occurs first)	
Organ Toxicity assessment		Q weekly	Q visits until 1 year

11.1.5 Study Assessments

Engraftment

Neutrophil engraftment will be measured by the number of days to reach a neutrophil count of greater than or equal 500/ul for three consecutive laboratory values obtained on different day. The day of engraftment will be the first day of the three consecutive laboratory values

Platelet engraftment will be measured by the number of days to reach a platelet count of greater than or equal 20,000/ul for three consecutive laboratory values obtained on different days independent of platelet transfusions the prior 7 days. The day of engraftment will be the first day of the three consecutive laboratory values.

Acute Graft-Versus-Host Disease

Acute graft-versus-host disease will be monitored daily and will be documented 1X / week from day +7 while patient is hospitalized for transplant. After discharge from hospital, Acute GVHD will be monitored and documented at a minimum of every 21 days till day +100 (or more if clinically indicated). Acute graft-versus-host disease will be graded according to the table shown in Appendix 1. Skin, gastrointestinal, and/or liver biopsies will be obtained, when appropriate, to facilitate the diagnosis. The type and duration of immunosuppressive treatment given for aGVHD will be recorded.

Chronic Graft-Versus-Host Disease

After day 100, patients will be assessed at least every 3 months (+/- 14 days) for cGVHD. cGVHD will be graded as mild, moderate, or severe based on the National Institutes of Health Consensus Development Project according to the table shown in Appendix II. The type and duration of immunosuppressive treatment given for cGVHD will be recorded.

Mucositis

Mucositis will be graded 3 times per week (Mon-Wed-Fri) by the mid-level provider or transplant physician from day 0 until day +28 or day of discharge (whichever occurs first) according to the WHO grading scale shown in Appendix III.

Total Parenteral Nutrition (TPN)

Start and stop dates of TPN will be recorded.

IV Pain Medications

Start and stop dates for the need for continuous IV infusion of narcotics for severe mucositis pain in the form of intravenous infusion or patient controlled analgesia (PCA) will be recorded.

Length of Hospitalization

Length of hospitalization will be measured from date of transplant to date of discharge.

Organ Toxicity

Information regarding renal, hepatic and pulmonary function will be collected at study entry and will be assessed throughout the time that the patient remains on GVHD prophylaxis. Patients will be assessed at least weekly until day 100 post transplant and then at follow up visits for 1 year post transplant for organ toxicity.

A patient will be considered to have liver dysfunction should the patient have a total bilirubin $\geq 3X$ the upper limit of normal and AST, ALT or alkaline phosphatase $\geq 5X$ the upper limit of normal.

Hepatic veno-occlusive disease will be diagnosed according to criteria set forth by McDonald et al [18]. Patient must have the presence, before day 20 after transplant, of at least two of the following features:

- Bilirubin greater than or equal to 2 mg/dL
- Hepatomegaly and right upper quadrant pain
- Ascites and/or unexplained weight gain greater than 2% from baseline.

A patient will be considered to have renal dysfunction should the patient have a serum creatinine $\geq 3X$ the baseline value, creatinine clearance or GFR $\leq 40\%$ of baseline or dialysis dependence.

A patient will be considered to have pulmonary toxicity based on the following criteria (using CTCAE v4):

- Bronchopulmonary hemorrhage, grade 3 or higher
- Pulmonary edema, grade 3 or higher
- Respiratory failure, grade 4 or higher

Overall Survival and Relapse-Free Survival

Both overall survival and relapse-free survival will be assessed one year from the day of stem cell infusion, T-O or death, which ever is first. One-year-relapse-free and overall survival will be defined by CIBMTR criteria for individual diseases. Suspicion for relapse should be confirmed by bone marrow biopsy and date of biopsy should serve as date of relapse. Biopsy is strongly encouraged but not required if there are compelling medical reasons why biopsy is not feasible or unobtainable or if relapse is otherwise evident and confirmed by peripheral blood flow cytometry.

Evaluation of Chimerism

Donor chimerism will be assessed by analysis of single-tandem repeats on whole marrow and in lymphocyte enriched or sorted CD3+ T cells and CD33+ granulocytes from the blood depending on institution practice. Blood will be obtained for donor chimerism “BME analysis” at approximately 1, 2, 3, 6, 9 and 12 months or as clinically indicated.

Infections

Documented bacterial, viral and fungal infections will be recorded for 1 year after transplantation.

12.0 MEASUREMENT OF EFFECT

12.1 Incidence, Length and Severity of Mucositis

The incidence, length and severity of mucositis from day 0 to day 28 (or discharge date if earlier) after allogeneic bone marrow transplantation comparing Tac, mini-dose MTX and MMF with Tac and MTX will be determined.

12.2 Rate of Neutrophil and Platelet Engraftment

Number of days to engraftment, for both neutrophil and platelet after allogeneic bone marrow transplantation comparing Tac, mini-dose MTX and MMF with Tac and MTX will be determined.

12.3 Incidence of Acute GVHD

The incidence and severity of grade II-IV and III-IV acute GVHD after allogeneic bone marrow transplantation comparing Tac, mini-dose MTX and MMF with Tac and MTX will be determined.

12.4 Secondary objective parameters will also be compared in the Tac, mini-dose MTX and MMF with the Tac and MTX:

- Length of hospitalization
- Length of use of TPN
- Incidence of infection in the first 100 days post-transplantation
- Incidence of hepatotoxicity in the first 100 days post-transplantation
- Incidence of nephrotoxicity in the first 100 days post-transplantation
- Incidence of pulmonary toxicity in the first 180 days post-transplantation
- Incidence and severity of chronic GVHD
- One year relapse-free survival
- Overall survival
- Chimerism results

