2.0 OBJECTIVES

2.1 Primary Objectives

- To determine the incidence, length and severity of mucositis from Day 0 until day of discharge or Day +28 (whichever comes first) after allogeneic bone marrow transplantation comparing Tac, mini-dose MTX and MMF with Tac and MTX.
- To study rates of neutrophil and platelet engraftment comparing Tac, mini-dose MTX and MMF versus Tac and MTX

- To study the incidence of acute graft-versus-host disease in HLA matched related and unrelated allogeneic bone marrow transplantation using a myeloablative preparative regimen comparing Tac, mini-dose MTX and MMF with Tac and MTX.

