2.2 Secondary Objectives

- Length of hospitalization/time to discharge
- Use of TPN (total parenteral nutrition)
- Length of time on continuous infusion narcotics
- Incidence of infection in the first 100 days post-transplantation
- Incidence of hepatotoxicity in first 100 days post-transplantation
- Incidence of nephrotoxicity in first 100 days post-transplantation
- Incidence of pulmonary toxicity in first 180 days post-transplantation
- Incidence and severity of grade II-IV and III-IV acute GVHD
- Incidence and severity of chronic GVHD
- One year relapse-free and overall survival

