14.0 STATISTICAL CONSIDERATIONS

Considering the potential for missed doses of methotrexate or other drug, this investigation will be based on an intent to treat analysis. This study hopes to show a reduction in the incidence of severe mucositis and time to neutrophil and platelet engraftment while not increasing the incidence or severity of acute GVHD in the allogeneic HCT population.

Our current rate of severe (grade 3-4) mucositis is 41%. Ninety-four (47 in each group) would be needed to demonstrate a 25% improvement in mucositis to 16%, based on a one-sided test with 5% significance and 80% power.

Our current estimate of mean day to neutrophil engraftment is 19 days. One hundred patients (50 in each group) would be needed to demonstrate a 4 day improvement in time to neutrophil engraftment based on a one-sided test with 5% significance and 80% power.

Our current percent of patients achieving platelet engraftment by day 21 is 26%. Ninety-eight (49 in each group) would be needed to demonstrate a 25% improvement in platelet engraftment to 51%, based on a one-sided test with 5% significance and 80% power.

Our current rate of any acute GVHD by day 60 is 62%. If the hazard ratio between treatment arms is at most 1.7, then we will conclude that the new treatment does not significantly increase acute GVHD. Forty-five patients per group are needed to detect this hazard ratio using a one-sided non-inferiority log-rank test with 5% significance and 80% power.

Therefore, this study requires 100 patients to have a minimum of 80% power to address all of the primary objectives.

Overall survival and progression-free survival will be estimated using the Kaplan-Meier method and compared between patients receiving Tac and MTX versus Tac, mini-MTX, and MMF using the log-rank test. Hospital stay will be compared between groups using the Wilcoxon rank sum test. TPN and 100-day incidence of complications will be compared using the Chi-square test. Acute and chronic GVHD will be estimated using cumulative incidence methods and compared using the Pepe-Mori test.

REFERENCES

1. Horan JT et al. Reducing the Risk for Transplantation-Related Mortality after Allogeneic Hematopoietic Cell Transplantation: How Much Progress Has Been Made? *JCO* 2011; 29: 805-813
2. Weisdorf D et al. Treatment of moderate/severe acute graft-versus-host disease after allogeneic bone marrow transplantation: an analysis of clinical risk features and outcome. *Blood* 1990; 75: 1024-1030

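### Section 12.3 measures the primary acute GVHD objective by grades that Section 2.2 calls secondary, while Section 14 sizes it on any grade by day 60, an endpoint with about 67% power rather than 80%

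*Combined protocol and SAP*

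**What the plan says.** Four places in the combined protocol and SAP bear on this endpoint.

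- **Section 2.1 (primary objectives):** "To study the incidence of acute graft-versus-host disease in HLA matched related and unrelated allogeneic bone marrow transplantation". No grade and no day are given.
- **Section 2.2 (secondary objectives):** "Incidence and severity of grade II-IV and III-IV acute GVHD".
- **Section 12.3 (measurement of effect):** "The incidence and severity of grade II-IV and III-IV acute GVHD", compared between arms, with no day. Sections 12.1 to 12.3 take mucositis, engraftment and acute GVHD in the order of the three primary objectives. Section 12.4 then begins "Secondary objective parameters will also be compared in the Tac, mini-dose MTX and MMF with the Tac and MTX", and its list omits acute GVHD.
- **Section 14 (sample size):** "Our current rate of any acute GVHD by day 60 is 62" percent. The next sentence sets the decision rule, "If the hazard ratio between treatment arms is at most 1.7", and the one after gives the size: "Forty-five patients per group are needed to detect this hazard ratio using a one-sided non-inferiority log-rank test with 5% significance and 80% power".

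Section 14 then states that 100 patients give at least 80% power for every primary objective. Its analysis sentence for GVHD names neither a grade nor a day: "Acute and chronic GVHD will be estimated using cumulative incidence methods and compared using the Pepe-Mori test". Section 11.1.5 has acute GVHD monitored and documented to day +100.

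**The concern.** The only grades that Section 12.3 measures are the ones Section 2.2 calls secondary. The only acute GVHD endpoint with a base rate and a sample size, any grade, appears nowhere in Section 12. Someone writing the analysis from Section 12.3 and someone writing it from Section 14 would produce different primary results.

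The difference matters clinically and statistically. Under Appendix I, grade I is skin stage 1-2 alone, so an any-grade endpoint includes mild skin disease that grades II-IV and III-IV leave out. The two kinds of result could point in different directions. They also rest on very different numbers of events, and events determine what a hazard ratio margin of 1.7 can show. This is the safety claim that accompanies the hoped-for gains in mucositis and engraftment, so its endpoint should be fixed in the text before the data are seen.

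**Working it through.** **Inputs.** Margin 1.7, one-sided 5%, 80% power, 62% by day 60 and 45 per group (Section 14); 1:1 allocation (Section 5.1); 50 per group with replacement of early drop-outs, so no inflation (Sections 3.2 and 3.3). The true hazard ratio is taken as 1, and all patients are assumed to be followed to the analysis day.

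**Step 1. Events needed (Schoenfeld, 1:1).**

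d = 4 × (1.645 + 0.842)² / (ln 1.7)² = 4 × 6.18 / 0.2816 ≈ 88. Freedman's formula gives 92.

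**Step 2. The plan's own figure.** Patients per group = events / event proportion / 2.

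| Assumed event proportion | Per group (Schoenfeld) |
|---|---|
| 62% in both arms (as stated) | 88 / 0.62 / 2 → 71 |
| 71.3% (mean of 62% and 1 − 0.38^1.7 = 80.7%) | 62 |
| 80.1% (62% extended to day 100 at constant hazard) | 55 |
| 99.7% (extended to one year at constant hazard) | 45 |
| 100% | 44 |

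The stated 45 per group comes out only if nearly every patient has an event. It does not follow from 62% by day 60.

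**Step 3. Power with 100 patients.** Power = Φ(½ × √events × ln 1.7 − 1.645).

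Any grade by day 60: 100 × 0.62 = 62 events. ½ × 7.874 × 0.5306 − 1.645 = 0.444, so power is about 67%.

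**Step 4. How much the unfixed day could matter.** At constant hazard to day 100, 80.1 events give ½ × 8.950 × 0.5306 − 1.645 = 0.73, or about 77%. Constant hazard after day 60 is an assumption, used only to show the direction and rough size.

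**Step 5. Graded endpoints, as illustration only.** The documents give no control-arm rate for grades II-IV or III-IV. The only rates available are those that Section 1.3 quotes for mini-dose methotrexate regimens.

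| Endpoint | Assumed rate | Events per 100 | Power against 1.7 |
|---|---|---|---|
| Grade II-IV | 59% | 59 | 65% |
| Grade II-IV | 33% | 33 | 45% |
| Grade III-IV | 17% | 17 | 29% |
| Grade III-IV | 5% | 5 | 15% |

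The 33-59% and 17% come from unrelated-donor transplants that included one-antigen mismatches. The 5% comes from reduced-intensity transplants. This trial is myeloablative and 8/8 matched, with standard-dose methotrexate as control.

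**The case against.** The best reply is that the plan can be read consistently apart from one section. The 1.7 rule directly follows the any-grade day-60 rate in the same paragraph of Section 14. Section 2.1 is ungraded, which fits any grade, and Section 2.2 puts the graded outcomes under secondary. On that reading Section 12.3 is a slip. It is not labelled primary either: its status is inferred from its place. Section 12 is also a loose list, since Section 12.4 omits continuous-infusion narcotics, which Section 2.2 includes, and adds chimerism, which Section 2.2 does not.

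Much of this stands. A reader might infer that the non-inferiority claim has no single endpoint, and that any grade, II-IV and III-IV all compete for the same 1.7 margin. The documents do not support that: no passage applies 1.7 to a graded endpoint, and only any-grade GVHD has a base rate and a sample size. Nor does monitoring to day +100 contradict a day-60 endpoint, because observing patients beyond the analysis window is ordinary.

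The reply does not remove the mismatch. Section 12.3 precedes the secondary list and matches the third primary objective in order, yet it names other grades. Day 60 qualifies only the historical rate, and no sentence makes it the analysis day. The single-endpoint reading therefore has to be inferred against the text of the measurement section. The reply also leaves the power shortfall untouched.

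**Conclusion.** The inconsistency is real but narrow. Section 12.3 disagrees with Sections 2.2 and 14 about which acute GVHD grades are primary, and the analysis day is not fixed anywhere. Any grade by day 60 is the most natural intended primary endpoint.

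For that endpoint the plan's inputs give about 62 events and about 67% power, against a stated 80% that needs about 88 events. This rests on the Schoenfeld approximation, a true hazard ratio of 1, 62% in both arms and complete follow-up to day 60. The ranges for graded endpoints (45-65% for II-IV, 15-29% for III-IV) rest on borrowed rates and model a test that the plan does not propose. They show only that the choice of grade matters, not what the power would be in this trial.

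**What to change.** 1. **Section 12.3:** define the primary endpoint as time to first acute GVHD of any grade by day 60, and state that only this endpoint carries the 1.7 non-inferiority claim.
2. **Section 12.4:** list grade II-IV and grade III-IV acute GVHD as secondary, consistent with Section 2.2, with one stated analysis day, reported as cumulative incidence with confidence intervals.
3. **Section 14:** replace the 45-per-group sentence. Say that 100 patients at 62% give about 62 events and about 67% power, and amend the statement that every primary objective has at least 80%. If 80% is to be kept at the same margin and rate, about 88 events are needed, which is 71 per group.
4. **If grade II-IV was the intended primary:** say so in Sections 2.1, 2.2 and 12.3, replace the 62% with a control rate for that grade, and restate the power from it.

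A separate matter to settle in the same edit is that Section 14 sizes with a non-inferiority log-rank test but analyses GVHD with the Pepe-Mori test. Naming the endpoint does not resolve that.

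The cost is protocol and SAP wording, with no new data if the sample size stays at 100. The graded results lose any primary status, and the plan must state a less favourable power for its GVHD safety claim.
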